12.1 SAMPLE SIZE RATIONALE

A sample size of 50 study subjects was chosen by the study sponsor.

12.2 SIGNIFICANCE LEVEL

Significance is defined at the p < 0.05 level based on a two-sided test.

12.3 DROP-OUT (PRODUCT TOLERABILITY) ASSESSMENT

Subjects who discontinue will be queried as to any side effects experienced by the study products.

12.4 SAFETY ASSESSMENT

Incidence of all adverse events reported during the study will be summarized. Tabulated summaries will include adverse events grouped by relation to study product.

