5. STUDY DESIGN OVERVIEW

Female or male subjects with acne prone skin will be enrolled in this split face single site study evaluating the barrier effects of Winlevi. Subjects who sign consent and meet all inclusion criteria and none of the exclusion criteria will be enrolled at the baseline visit. Subjects will be asked to continue their own, self-selected cleanser and sunscreen throughout the 2-week study with equal application to both sides of the face. The sunscreen and cleanser must have been used for 30 days prior to study enrollment without difficulty. Subjects must apply Winlevi twice daily to the randomized right or left face.

Subjects will receive a compliance diary and the blinded study treatment product to be applied to the randomized half face following cleansing, every morning and evening. The assessing dermatologist investigator will be blinded as to which side of the face is receiving the Winlevi treatment. Subjects will be seen at baseline, 24 hours, week 1, and week 2. The dermatologist investigator and subjects will assess tolerability for each side of the face separately at each visit on a 5 point ordinal scale. Noninvasive TEWL and corneometry assessments of both sides of the face will be conducted at baseline, 24 hours, week 1, and week 2.

Subjects will complete their study participation at week 2. The compliance diary and all study products will be collected at this time. Women of child bearing potential will be administered a urine pregnancy test at baseline and week 2.

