8.3 NONCOMPLIANT SUBJECTS

Subjects who are found to be noncompliant will be queried as to the reason for their noncompliance. If noncompliance results from study product problems, full interviews will be conducted by the investigator to determine the nature and severity of the problem and an adverse event will be recorded. Subjects who are noncompliant will be released from their study participation and their last visit data carried forward.

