11.2 ADVERSE EXPERIENCES

An adverse experience is defined as any untoward medical occurrence (sign, symptom or laboratory finding), regardless of severity and whether or not attributed to the study product.

The investigator/coordinator will report all adverse experiences (AEs) that occur throughout the study. All AEs will be recorded in the appropriate AE log. The report will include: date of onset, a description of the AE, severity, seriousness, action taken, relationship to the study drug, outcome of the event, and date of resolution.

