11.2.1 ASSESSMENT OF SEVERITY

The intensity or severity of an AE is characterized as:Mild:AE which is easily tolerated.Moderate:AE sufficiently discomforting to interfere with daily activity.Severe:AE which prevents normal daily activities.

Subjects who are withdrawn from the study due to any AE will be followed by the investigator until the outcome is determined. The investigator will summarize and will document all information relating to the AE and follow up.

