11.2.2 RELATIONSHIP TO STUDY PRODUCT

The relationship is characterized as:

Not Related - applies to any adverse experience that is clearly not related to use of the study product.

Possible - means the association of the adverse experience with the study product is unknown; however, a relationship between study product and experience cannot be ruled out.

Probable - there is a reasonable temporal relationship between the use of the study product and the adverse experience. Based upon the investigator's clinical experience, the association of the event with the study product seems likely.

Definite - The AE occurs following the application of the study product and it cannot be reasonably explained by any other known characteristics of the subject's clinical state, environmental or toxic factors, or other modes of therapy administered to the subject. It disappears or decreases upon discontinuation of the study product and reappears on a re-challenge of the study product. This is necessary to evaluate allergic or irritant contact dermatitis.

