Please let us know if you are experiencing any of these problems. Please use the following scale: 0=none, 1=minimal, 2=mild, 3=moderate, 4=severe. A lower number means you do not have the problem. Circle your correct response. Please rate both your cheeks separately.

Ask the study staff if you have any questions.

RIGHT CHEEK

Visits	Baseline	24 Hours	Week 1	Week 2
Dryness	01234	01234	01234	01234
Tightness	01234	01234	01234	01234
Stinging	01234	01234	01234	01234
Itching	01234	01234	01234	01234
Burning	01234	01234	01234	01234

LEFT CHEEK

Visits	Baseline	24 Hours	Week 1	Week 2
Dryness	01234	01234	01234	01234
Tightness	01234	01234	01234	01234
Stinging	01234	01234	01234	01234
Itching	01234	01234	01234	01234
Burning	01234	01234	01234	01234

NONINVASIVE ASSESSMENTS

	Baseline	24 Hours	Week 1	Week 2
TEWL Right Cheek				
TEWL Left Cheek				
Corneometry Right Cheek				
Corneometry Left Cheek				

ADVERSE EVENT

Did the subject experience any adverse event? Yes or No *If yes, list below:

Adverse Event	1	2
Start Date mm/dd/yy		
Stop Date mm/dd/yy		
Ongoing*		
Frequency ¹		
Severity ²		
Relation to Study Med ³		
Action Taken ⁴		
Outcome ⁵		
Serious (Y/N)		
¹ Frequency ² Severity 1=Continuous 1=Mild 2=Intermittent 2=Moderate 3=Isolated 3=Severe	³ Relation to Study Med 1=Not related 2=Possible 3=Probable 4=Definite	⁴ Action Taken (insert all codes that apply) 1=None 2=Study drug discontinued 3=Non-drug therapy 4=New OTC or R _x drug added

⁵Outcome

1=Resolved

2=Improved

3=Stabilized

4=Ongoing

5=Worsened

6=Lost to follow-up

*Check only if the adverse event is ongoing when subject completes/exits the study.

**Refer to the protocol for definitions of severity and relationship to study product.

Final Subject Status				
The s	ubject completed the study. Date Completed: Month Day	Year		
The streason:	ubject discontinued the study prematurely due to the following O	DNE		
	Date Discontinued: Month Day	Year		
discontinua	Adverse event, including intercurrent illness, which required study tion (specify) Protocol violation (specify)	-		
	Lost to follow-up Subject decision/withdrawal of consent			
	Other (specify)	?		

Investigator's State	ement:
information record	pages of this case report form. To the best of my knowledge, the led on the case report form is a complete and accurate record of ment course during the study.
Signature	Printed Name
Date Signed:	nth Day Year

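### The AE form does not ask which side of the face is affected and Section 12.4 plans no by-side table, so the planned AE summaries do not use the untreated side as a control (minor)

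*Combined protocol and SAP*

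**What the plan says.** Section 7.1.4 has each subject use Winlevi on one randomized side of the face. Sections 12.5.1 and 12.5.2 define both endpoints against the untreated side.

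For AEs, Section 12.4 plans an overall incidence summary and then: "Tabulated summaries will include adverse events grouped by relation to study product". It names no other AE table.

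Section 11.2 sets the content of the AE report: the onset date, followed by "a description of the AE, severity, seriousness, action taken, relationship to the study drug, outcome of the event, and date of resolution". The AE form in Appendix I opens with "Did the subject experience any adverse event" and then gives rows for each event.

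Relatedness is graded under Section 11.2.2. The probable category, for example, reads in part: "Based upon the investigator's clinical experience, the association of the event with the study product seems likely". Section 5 states: "The assessing dermatologist investigator will be blinded as to which side of the face is receiving the Winlevi treatment".

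Three further places could bring out AE detail. Section 8.3, for product-related noncompliance, says that "full interviews will be conducted by the investigator to determine the nature and severity of the problem and an adverse event will be recorded". Section 11.2.1, for subjects withdrawn because of an AE, says: "The investigator will summarize and will document all information relating to the AE and follow up". Section 12.3 says: "Subjects who discontinue will be queried as to any side effects experienced by the study products".

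**The concern.** In a split-face design, comparing the two sides within a subject separates a product effect from background reactivity. An AE table that counts each subject once, whichever side reacted, gives that comparison up. An excess confined to the treated side and an even spread over both sides would give the same incidence figure.

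The form matters more than the table. A table can be added at any time before reporting, but a side that nobody wrote down may not be recoverable. The AE form is also the exception within its own appendix, because the tolerability and biomeasurement forms are all laid out right and left.

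**Working it through.** The plan states no figure on this point, so there is none to reproduce. The check sets the text side by side.

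**1. Is side or location collected for AEs?**
- AE report, Section 11.2, eight items: onset, description, severity, seriousness, action, relationship, outcome, resolution. Items for side or location: 0 of 8.
- AE form, Appendix I, ten rows: event, start date, stop date, ongoing, frequency, severity, relation, action, outcome, serious. Rows for side or location: 0 of 10.

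**2. Is a by-side AE table planned?** Section 12.4 names overall incidence and grouping by relatedness. By-side tables named: 0. If k of 50 subjects have a facial AE on one side only, they contribute k/50 to incidence for every split from k v 0 to 0 v k.

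**3. Does the relatedness table stand in for side?** Not reliably. The grade rests on clinical judgement (Section 11.2.2), and the assessing investigator does not know the treated side (Section 5). Subjects do know it: they apply product to one side only, and it is labelled left or right (Section 10.3). They may convey the side when they describe an event. Some side information may therefore enter the relatedness grade, but in an uncontrolled way.

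**4. What do the per-side scores already cover?** The investigator scores four signs and the subject five symptoms (Section 8.1), so 4 + 5 = 9 scores per side at each of four visits. Section 12 plans Wilcoxon signed rank and sign tests on them. Most local reactions are therefore compared by side outside the AE tables.

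**5. What may those scores miss?**
- *Between visits.* Scores are taken at baseline, 24 hours, week 1 and week 2, so the gaps are 1, 6 and 7 days. A reaction could arise and clear within one.
- *Forehead and jawline.* Product is applied there as well as to the cheek (Section 10.3). Section 8.1 speaks of the side of the face, but the score forms are headed by cheek and subjects are told to rate their cheeks. This route exists only if the forms are followed literally.
- *Before an early stop.* A reaction may arise after the last scored visit. For noncompliant subjects, Section 8.3 carries the last visit's data forward.

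**6. What could still recover the side?** Six routes: the free-text description (Section 11.2), diary comments (8.2), the noncompliance interview (8.3), the AE follow-up notes (11.2.1), the discontinuation query (12.3) and the final evaluations sought at early termination (9.1). The code held until data lock (10.6) would then turn right or left into treated or untreated. None of these routes asks for side in the text available. The diary is a separate file, so whether it prompts for side is unknown.

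**The case against.** The best case against acting is that the plan already compares the sides where it matters. The objective in Section 4 is defined by corneometry and TEWL, not by AE counts. Local reactions are scored per side and tested as paired data. Systemic AEs have no side. Overall incidence with relatedness is a coherent safety summary, and the wording of Section 12.4 does not exclude further tables. Section 11.1 describes skin irritation as rare, so a by-side AE table would hold few events. The forehead and jawline gap could be closed for the scored signs simply by correcting the form headings.

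Most of this stands, and it is why the point is minor. It does not answer the form: a further table is allowed, but it needs side data that nobody is required to record. Correcting the headings would not help with reactions between visits or after the last scored visit.

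A reader might infer several stronger things that the documents do not support:
- *That the trial cannot compare local reactions between sides.* It can, through the per-side scores.
- *That side is lost for every AE.* Six routes may carry it.
- *That blinding leaves the relatedness table with no information on side.* Subjects know the treated side, Section 11.2 has the investigator or coordinator report AEs, and the documents do not say whether the coordinator is blinded. The blinding itself is correct.
- *That a formal by-side AE test is missing.* With five one-sided events, all on the treated side, the exact two-sided p-value is 2 × 0.5^5 = 0.0625, so fewer than six cannot reach the plan's 0.05 level. With irritation called rare, a test would add little.

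**Conclusion.** The point holds as a minor, inexpensive improvement. As written, the plan gives AE tables that do not compare treated-side with untreated-side facial events, because side is not a required item and no by-side table is named.

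The gap covers only facial reactions that the per-side scores may miss, and the free-text, diary and exit routes narrow it further. The documents give no AE rate by side, so no number is put on it. The primary endpoint, the secondary endpoint and the tolerability tests are unaffected.

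The conclusion rests on two readings: that the AE form shown is the form in use, and that the diary, which is not available here, does not already prompt for side and location. If the diary does, the between-visit part shrinks further.

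**What to change.** 1. Add two tick-box items per event to the AE form, completed without knowledge of the treated side: right / left / both / not facial, and forehead / cheek / jawline.
2. Add to Section 12.4: *After data lock, the number of subjects with a facial AE on the treated side only, the untreated side only, or both will be tabulated descriptively.*
3. Keep the relatedness table unchanged. No formal test is needed.

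The cost is two fields and one table produced after data lock. It needs no extra visit or measurement and no unblinding during the trial. The downside is that few events are expected, so the table will be sparse and can only be read descriptively.

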12.5 ENDPOINTS

12.5.1 PRIMARY EFFICACY ENDPOINT

The primary endpoint is the change in corneometry reading between the side of the face treated with Winlevi versus no treatment.

12.5.2 SECONDARY EFFICACY ENDPOINT

The secondary endpoint is the change in TEWL reading between the side of the face treated with Winlevi versus no treatment.

13. ETHICS

13.1 INFORMED CONSENT

The principles of Informed Consent, according to FDA Regulations and ICH step 5 guidelines on GCPs, will be followed.

Subjects must provide written informed consent prior to any study procedures being completed. Subject signed informed consents will be kept on file by the Investigator for Regulatory Authorities' inspection at any time. A copy of the signed and dated consent forms will be given to the subject.

13.2 INSTITUTIONAL REVIEW BOARD (IRB)

The study documents will be submitted to an IRB selected by Dermatology Consulting Services for approval to ensure the safety of the human subjects enrolled in the study.

13.3 SUBJECT CONFIDENTIALITY

All participants are concerned for the individual subject's privacy and, therefore, all subject results will be identified only by a subject identification number. However, in compliance with federal guidelines regarding the monitoring of clinical studies and in fulfillment of his/her obligations to the Sponsor, it is required that the Investigator permit the study monitor and/or FDA representative to review that portion of the subject's medical record that is directly related to the study. This shall include all study relevant documentation including subject medical histories to verify eligibility, laboratory test result reports to verify transcription accuracy, admission/discharge summaries for hospital stays occurring while the subject is enrolled in the study, and autopsy reports for deaths occurring during the study.

As part of the required content of informed consent, the subject must be informed that his/her medical chart may be reviewed by the sponsor, the Sponsor's authorized representative, or a representative of the FDA. Should access to the medical record require a separate waiver or authorization, it is the investigator's responsibility to obtain such permission from the subject in writing before the subject is entered into the study.

14. DOCUMENTATION

14.1 SITE DOCUMENTS REQUIRED FOR INITIATION

Prior to the initiation of the study, the following items must be received:

- a) Sponsor approval of study
- b) Current curriculum vitae of the Principal Investigator
- c) Copy of Principal Investigator's Medical license
- d) A signed copy of the protocol Investigator's Agreement page
- e) Original Non-Disclosure Agreement
- f) Signed Budget Agreement

14.2 STUDY DOCUMENTS SUPPLIED BY THE SPONSOR

Dermatology Consulting Services will provide all study documents.

14.3 MAINTENANCE AND RETENTION OF RECORDS

The study activities will be conducted according to Good Clinical Practices as outlined in ICH step 5 guidelines by the Food and Drug Administration. It is the responsibility of the Investigator to maintain a comprehensive and centralized filing system of all relevant documentation.

Investigators will be instructed to retain all study records required by the sponsor, as well as the regulations, in a secure and safe facility with limited access. Regulations require retention for a period of at least two years after last marketing approval and notification from the sponsor. These regulatory

documents should be retained for a longer period if required by local regulatory requirements.

Archiving of data - Copies of all pertinent records will be retained by the investigator for at least two years following final approval of the drug and/or notification from the sponsor. These records include documents pertaining to the receipt and return of drug supplies, IRB, Informed Consent, as well as final signed case report forms. No documents shall be transferred from the site or destroyed without first notifying the sponsor. The sponsor will archive the data for the lifetime of the product.

14.3.1 CASE REPORT FORMS (CRF)

CRFs for individual subjects will be provided and completed by Dermatology Consulting Services, as appropriate. CRFs must be legible and complete.

CRFs must be completed and signed by the investigator for each subject enrolled, including those removed from the study for any reason. The reason for removal must be noted on the study conclusion CRFs by the investigator for each subject. CRFs must be kept current to reflect the subject's status at each phase during the course of the study. Subjects are not to be identified on CRFs by name; appropriately coded identification and the subject's initials must be used. The investigator must keep a separate log of the subject's names and addresses.

The research site will maintain the following documents:

- 1. Subject Screening Logs: Logs will reflect the reason any subject screened for the study was found to be ineligible.
- 2. Study Personnel Signature Logs: Logs will contain all site personnel along with their responsibilities and signatures. Logs will be maintained at the site throughout the study.
- 3. Monitoring Logs: Logs will contain the date and purpose of all monitoring visits by the Sponsor.
- 4. Enrollment Logs: Logs will contain subject initials and start and end dates for all subjects enrolled.
- 5. Product Inventory / Packing Slip Logs: Logs will reflect the total amount of study product shipped to the site and received and signed for by the Investigator.
- 6. Product Accountability Logs: Logs will reflect the total amount of study product dispensed to and returned by each subject.

14.3.2 MONITORING

The study activities will be monitored by a Sponsor appointed representative, if desired.

14.4 PROTOCOL MODIFICATION

The procedures defined in the protocol and in the CRF will be carefully reviewed to ensure that all parties involved with the study fully understand the protocol. In order to ensure the validity of the data, no deviations from the protocol may be made unless the issue is broad enough to warrant revision of the protocol. Such revisions must be submitted to and have approval in writing from the Sponsor and the IRB prior to implementation.

14.5 AUDITS/INSPECTIONS

During the course of the study and/or after it has been completed, one or more site visits may be undertaken by auditors as authorized representatives of the Sponsor.

APPENDIX I: CASE REPORT FORMS

The following documents are attached:

- 1. Screening Questionnaire
- 2. Inclusion/Exclusion Criteria
- 3. Investigator Questionnaires Tolerability
- 4. Subject Questionnaires Tolerability
- 5. Adverse Event Assessment
- 6. Study Termination
- 7. Informed Consent Form (as a separate file)
- 8. Subject Diary (as a separate file)

SCREENING QUESTIONNAIRE

DATE			
NAMELAST	FIRST	MIDDLE INITIA	AL
DATE OF BIRTH			AGE
SOCIAL SECURITY			
GENDER AT BIRTH		RACE	
STREET ADDRESS			
CITY	STA	ТЕ	ZIP
E-MAIL			
CELL PHONE ()	_	CELL PHONE	CARRIER
EMERGENCY CONTACT		RELATIONSH	[IP
EMERGENCY CONTACT	-		

I understand federal law requires any person who receives more than \$600 in a calendar year from our office must be issued a 1099 tax form. I understand I must provide my social security number to participate in this study.

SIGNATURE

DATE_____

INCLUSION/EXCLUSION CRITERIA

Inclusion Criteria:

- 1. Subjects who self identify as having sensitive acne prone skin.
- 2. Female or male subjects 18+ years of age.
- 3. Subjects with Fitzpatrick skin types I-VI.
- 4. Subject agrees not to introduce any new colored cosmetics (lipsticks, eye shadows, facial foundations, blush, powder) or skin care products during the study.
- 5. Subjects must be willing to use only a cleanser and sunscreen on the entire face and no other skin care products.
- 6. Subjects must be willing to use the Winlevi study product to designated half face. No other topical acne treatment products on the entire face for the 2 week duration of the study.
- 7. Subject has signed an Informed Consent Form in compliance with 21CFR Part 50: "Protection of Human Subjects."
- 8. Subject is dependable and able to follow directions and is willing to comply with the schedule of visits.
- 9. Subject is in generally good physical and mental health.

Exclusion Criteria:

- 1. Any dermatological disorder, which in the investigator's opinion, may interfere with the accurate evaluation of the subject's skin characteristics, except for the conditions associated with sensitive skin.
- 2. Subjects who are not willing to use only the assigned study product and nothing else one randomized half face, except for cleanser and sunscreen that must remain unchanged during the study. Moisturizers or topical acne treatment products should not be used during the 2 week study period on either side of the face.
- 3. Subjects who do not agree to refrain from direct sun exposure during the study duration.
- 4. Subjects who have demonstrated a previous hypersensitivity reaction to any of the ingredients of the study products.
- 5. Subjects, who are pregnant, breast feeding, or planning a pregnancy.
- 6. Subjects with clinically significant unstable medical disorders.
- 7. Subjects who are unwilling or unable to comply with the requirements of the protocol.
- 8. Subjects who have history of a psychological illness or condition that would interfere with their ability to understand and follow the requirements of the study.
- 9. Subjects who are currently participating in any other clinical study.
- 10. Subjects with any planned surgeries and/or invasive medical procedures during the course of the study.
- 11. Subjects who currently or frequently use high doses of anti-inflammatory drugs for a defined medication condition. Aspirin use should not exceed 2 tablets (650 mg) per day.
- 12. Subjects currently receiving any anticancer, immunosuppressive treatments/ medications (e.g., azathioprine, belimumab, cyclophosphamide, Enbrel, Imuran, Humira, mycophenolate mofetil, methotrexate, prednisone, Remicade, Stelara.), or radiation as determined by the initial paperwork.
- 13. Subjects with a history of immunosuppression/immune deficiency disorders (including (HIV infection or AIDS) or currently using immunosuppressive medications (e.g., azathioprine, belimumab, cyclophosphamide, Enbrel, Imuran, Humira, mycophenolate mofetil, methotrexate, prednisone, Remicade, Stelara) and/or radiation as determined by study documentation.

All inclusion criteria must be met and none of the exclusion criteria. Circle any inclusion criteria that are not met and any exclusion criteria that are met and declare the subject a screening failure. I certify all inclusion criteria have been met and none of the exclusion criteria have been met.

[name] Primary Investigator Date

INVESTIGATOR TOLERABILITY ASSESSMENT

RIGHT CHEEK

Visits	Baseline	24 Hours	Week 1	Week 2
Dryness	01234	01234	01234	01234
Erythema	01234	01234	01234	01234
Scaling	01234	01234	01234	01234
Irritation	01234	01234	01234	01234

LEFT CHEEK

Visits	Baseline	24 Hours	Week 1	Week 2
Dryness	01234	01234	01234	01234
Erythema	01234	01234	01234	01234
Scaling	01234	01234	01234	01234
Irritation	01234	01234	01234	01234

0=none, 1=minimal, 2=mild, 3=moderate, 4=severe

SUBJECT TOLERABIILTY ASSESSMENT

Please let us know if you are experiencing any of these problems. Please use the following scale: 0=none, 1=minimal, 2=mild, 3=moderate, 4=severe. A lower number means you do not have the problem. Circle your correct response. Please rate both your cheeks separately.

Ask the study staff if you have any questions.

RIGHT CHEEK

Visits	Baseline	24 Hours	Week 1	Week 2
Dryness	01234	01234	01234	01234
Tightness	01234	01234	01234	01234
Stinging	01234	01234	01234	01234
Itching	01234	01234	01234	01234
Burning	01234	01234	01234	01234

LEFT CHEEK

Visits	Baseline	24 Hours	Week 1	Week 2
Dryness	01234	01234	01234	01234
Tightness	01234	01234	01234	01234
Stinging	01234	01234	01234	01234
Itching	01234	01234	01234	01234
Burning	01234	01234	01234	01234

NONINVASIVE ASSESSMENTS

	Baseline	24 Hours	Week 1	Week 2
TEWL Right Cheek				
TEWL Left Cheek				
Corneometry Right Cheek				
Corneometry Left Cheek				

ADVERSE EVENT

Did the subject experience any adverse event? Yes or No *If yes, list below:

Adverse Event	1	2
Start Date mm/dd/yy		
Stop Date mm/dd/yy		
Ongoing*		
Frequency ¹		
Severity ²		
Relation to Study Med ³		
Action Taken ⁴		
Outcome ⁵		
Serious (Y/N)		
¹ Frequency ² Severity 1=Continuous 1=Mild 2=Intermittent 2=Moderate 3=Isolated 3=Severe	³ Relation to Study Med 1=Not related 2=Possible 3=Probable 4=Definite	⁴ Action Taken (insert all codes that apply) 1=None 2=Study drug discontinued 3=Non-drug therapy 4=New OTC or R _x drug added

⁵Outcome

1=Resolved

2=Improved

3=Stabilized

4=Ongoing

5=Worsened

6=Lost to follow-up

*Check only if the adverse event is ongoing when subject completes/exits the study.

**Refer to the protocol for definitions of severity and relationship to study product.

Final Subject Status				
The s	ubject completed the study. Date Completed: Month Day	Year		
The streason:	ubject discontinued the study prematurely due to the following O	DNE		
	Date Discontinued: Month Day	Year		
discontinua	Adverse event, including intercurrent illness, which required study tion (specify) Protocol violation (specify)	-		
	Lost to follow-up Subject decision/withdrawal of consent			
	Other (specify)	?		

Investigator's State	ement:
information record	pages of this case report form. To the best of my knowledge, the led on the case report form is a complete and accurate record of ment course during the study.
Signature	Printed Name
Date Signed:	nth Day Year

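### The investigator and subject tolerability forms print all four visits side by side and nothing keeps earlier scores from the rater, so follow-up ratings may be anchored to them

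*Combined protocol and SAP*

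**What the plan says.** Section 8.1 has the investigator rate four signs and the subject rate five symptoms, separately for each side of the face, on a five-point scale from 0 (none) to 4 (severe). This is done at baseline, 24 hours, week 1 and week 2.

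Appendix I supplies the forms. Under "INVESTIGATOR TOLERABILITY ASSESSMENT" there is one grid for the right cheek and one for the left, each with the header row "Visits Baseline 24 Hours Week 1 Week 2". The subject form has the same layout and speaks to the subject directly: "Circle your correct response. Please rate both your cheeks separately".

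Section 14.3.1 says "CRFs must be kept current to reflect the subject's status at each phase during the course of the study". It does not say whether each visit starts on a clean copy.

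Section 5 gives the masking of the investigator: "The assessing dermatologist investigator will be blinded as to which side of the face is receiving the Winlevi treatment". Neither Section 5 nor the visit instructions in Section 7.2 say whether earlier scores are available at rating.

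Section 12 analyses the investigator and subject ratings with the Wilcoxon signed rank test and the sign test for paired comparisons. Section 12.2 sets significance at p < 0.05, two-sided.

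**The concern.** The 0-4 scale is a static severity scale. Each grade describes the skin, or the sensation, as it is on the day, so a rater needs no earlier score to use it. A grid that shows earlier scores adds information the rating does not require, and it makes repeating the adjacent number easy. The scale is coarse, so one step not recorded is a whole grade. The first follow-up comes only 24 hours after baseline.

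The direction matters here. The study hopes to show that the product does no harm to the skin, and the ratings are tested for a difference with no margin stated. In that setting, a recording habit that mutes change makes a non-significant tolerability comparison more likely and makes mean differences look smaller. Scores that were anchored when recorded cannot be corrected in the analysis.

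**Working it through.** The documents give no tolerability effect size, standard deviation or margin, so there is no stated figure to reproduce. The check has three parts.

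**1. What is exposed if the forms are used as printed**

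- Items: 4 investigator signs and 5 subject symptoms (Section 8.1 and Appendix I).
- Cheeks: 2. Visits: 4, of which 3 have earlier columns already filled.
- All scores per subject: (4 + 5) × 2 × 4 = 72.
- Investigator scores recorded beside an earlier one: 4 × 2 × 3 = 24.
- Subject scores recorded beside an earlier one: 5 × 2 × 3 = 30.
- Total exposed: 24 + 30 = 54 of 72, or 75%. Only the baseline scores are free of it.
- At week 2 each score stands beside three earlier ones.

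**2. Whether any section prevents it**

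- Appendix I: one four-visit grid per cheek on both rating forms.
- Section 14.3.1: one set of CRFs per subject, kept up to date through the study. No separate page per visit is mentioned.
- Section 7.2: each visit repeats the rating instruction, with nothing on access to earlier scores.
- Section 5: masking covers the treated side, for the investigator only.

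No section contains a safeguard. No section states that the completed grid lies in front of the rater either.

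**3. Direction of the bias, if there is anchoring**

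A simple model: recorded follow-up score = (1 − a) × true follow-up score + a × baseline score, where a is the degree of pull and is unknown.

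- Recorded change on one cheek = (1 − a) × true change.
- Recorded difference in change between cheeks = (1 − a) × true difference in change.
- Recorded difference between cheeks at a visit = (1 − a) × true difference + a × baseline difference. The side is randomised, so the baseline term averages about zero and the mean again shrinks by (1 − a).

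For any a between 0 and 1, the mean difference is biased toward zero, whichever paired comparison Section 12 intends.

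The effect on the tests depends on how the pull works:

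- If it is strictly proportional, the spread of change shrinks by the same factor: (1 − a) × mean divided by (1 − a) × SD equals mean divided by SD. Before rounding to whole grades, the signs and ranks of the change differences are unaltered, so a test on change from baseline loses nothing.
- If true one-grade worsenings are simply recorded as no change, pairs that would have shown a difference become ties, and the sign and signed rank tests lose information.

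The documents do not say which applies or how large a would be, so no power figure can be supported.

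**The case against.** The strongest reply is that visibility is inferred from the layout. Section 14.3.1 sets a record-keeping duty; it does not describe how ratings are captured. The site may use a clean copy at each visit, or transcribe scores from elsewhere. This stands, and the point is therefore conditional. It is weaker for the subject form, whose wording shows that the subject circles answers directly on the four-visit grid.

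A second reply is that the direction is not certain. A rater who expects a trend could exaggerate it when earlier scores are visible. Subjects may be prone to this, since the documents describe product on one side only and they would know which side it is. This also stands. Anchoring toward no change is a credible risk and has not been demonstrated.

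A third is that these ratings do not carry the study's main claim. Section 4 defines lack of barrier damage through corneometry and TEWL, and Sections 12.5.1 and 12.5.2 make those readings the primary and secondary endpoints. That is right, and it limits how much weight the point deserves. The ratings are still formally tested under Section 12.

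A reader might go further and infer that the instrument readings are affected too, because the form headed "NONINVASIVE ASSESSMENTS" also lists the four visits side by side. The documents do not support that. TEWL and corneometry are device outputs, and a neighbouring column cannot pull them as it can pull a judgement. The only route would be selective repeat readings, and the documents describe no repeats and do not say who operates the devices.

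**Conclusion.** The point holds as a limited one. Both rating forms print four visits side by side, no section keeps earlier scores from the rater, and if the forms are used as printed, 54 of 72 tolerability scores per subject are recorded with earlier scores in view. Those ratings may be anchored. If they are, the recorded between-cheek difference shrinks toward zero, which favours a result of no difference in tolerability.

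This rests on two assumptions that the documents neither confirm nor exclude: that the completed grid is at hand at later visits, and that visible scores pull toward repetition more than they exaggerate an expected trend. The size is unknown.

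A reader might infer that the primary result is biased, or that a definite amount of power is lost. Neither follows: the primary endpoint is an instrument reading, and the inputs for a power loss are not in the documents. The point is an inexpensive improvement to the tolerability data and does not bear on the validity of the corneometry or TEWL comparison.

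**What to change.** - Split the investigator and subject tolerability forms in Appendix I into one page per visit, each page holding both cheeks.
- Collect each page at the end of the visit, and keep earlier pages from the rater until the new page is complete.
- State this in Section 7.2 or Section 8.1. If the site already uses clean copies, one sentence saying so settles the matter.
- Leave change from baseline to be computed in the analysis.

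The cost is four short pages in place of one table per form, slightly more paper or data entry, and the loss of a side-by-side view for the rater. No visit, measurement or planned test changes.
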